3.3.2 Follow-up for withdrawn subjects

Describe when and how to withdraw subjects from the study; the type and timing of the data to be collected for withdrawal of subjects; whether and how subjects are to be replaced; the follow-up for subjects withdrawn from investigational treatment.

Study personnel will contact consenting parents by phone notifying them of their removal from the study and the reason for withdrawal. If the reason is due to failure-to-thrive, the infant's pediatrician will also be notified. If study personnel are unable to reach the consenting parent, a letter will be sent via US mail.

No further data will be collected on participants that are withdrawn, and these participants will not be replaced.

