3.3 Early Withdrawal of Subjects

3.3.1 Criteria for removal from study

Insert subject withdrawal criteria (e.g., safety reasons, failure of subject to adhere to protocol requirements, subject consent withdrawal, disease progression, etc.).

1. Infants exhibiting failure-to-thrive defined as:
 - a. Weight-for-length $< 5^{\text{th}}$ percentile for sex and age on the WHO growth chart
 - b. Downward crossing of > 2 major centile lines on the WHO growth chart (relevant major lines include 95th, 90th, 75th, 50th, 25th, 10th, 5th) after enrollment
2. Non-adherence to the study visit schedule characterized by failing to complete **two** scheduled study intervention visits within 2 weeks of turning 1, 2, 3, 4, and 5 months old (does not include enrollment and final visit)

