7.1 Study Design

Describe and explain the study design.

This study is a randomized, clinical trial involving 60 exclusively formula fed infants born at ≥ 37 weeks gestational age who are at-risk for overweight based upon maternal pre-pregnancy overweight or obesity (or alternatively at first prenatal visit if pre-pregnancy weight/height not known) and infant birthweight $\geq 50^{\text{th}}$ percentile. Infants will be enrolled at Penn State Health Children's Hospital or at affiliated clinics within the Division of Academic General Pediatrics between birth and age 1 month, where they will be randomized to a calibrated formula intake intervention or control. Participating infants in the intervention group will be seen monthly until age 6 months where they will be weighed and measured, and parents will complete surveys related to volume of formula consumed, infant appetite, parent feeding style, and infant temperament. Control infants will follow the same procedures, but will not have scheduled visits at ages 3 and 5 months. Instead their visits will correspond to usual care well child visits at ages 1, 2, 4, and 6 months.

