informed of the volume to expect at the subsequent visit in one month should the child maintain the same weight-for-age percentile, again with a 10% reduction.

10% was chosen for this pilot because it balances feasibility (relatively likely that parents can comply) and safety (unlikely to cause failure-to-thrive by reducing total daily formula volume by ~3 ounces)

6. Parents will be given instruction to prepare the formula volume in each bottle on the lower end of what they anticipate the infant will eat. For example, if they anticipate the infant will consume 3-4 ounces per feed, they will prepare 3 ounces at first. If hunger cues persist, they will then prepare an additional 1-2 ounces of formula.

7.2.3 Visit 3

Age 2 Month Visit (42-77 days)

Both study groups:

1. Anthropometrics of infant (weight, recumbent length)
2. Diary cards to be completed for the 3 days following the visit
3. Diary cards to be completed x 3 days prior to next study visit

Intervention group only:

1. Recommend formula volumes for the next month based on Visit 2 procedures
2. **If, for a second consecutive month, the child has WFL \geq 75th percentile on the WHO WFL growth chart**, recommended daily formula volumes will be calculated based upon the child's current age, weight, and energy requirement (kcal/kg/day) with a 15% reduction in daily volume. Further, parents will be informed of the volume to expect at the subsequent visit in one month should the child maintain the same weight-for-age percentile, again with a 15% reduction.

7.2.4 Visit 4

Age 3 Month Visit (78-109 days): Intervention group only

1. Anthropometrics of infant (weight, recumbent length)
2. Diary cards to be completed for the 3 days following the visit
3. Diary cards to be completed x 3 days prior to next study visit
4. Recommend formula volumes for the next month based on Visit 2 and 3 procedures

7.2.5 Visit 5

Age 4 Month Visit (110-140 days)

Both study groups:

1. Anthropometrics of infant (weight, recumbent length)
2. Diary cards to be completed for the 3 days following the visit
3. Diary cards to be completed x 3 days prior to next study visit

Intervention group only:

4. Recommend formula volumes for the next month based on Visit 2 and 3 procedures

5. Provide handouts on soothing fussy infants, feeding

7.2.6 Visit 6

Age 5 Month Visit (141-171 days) – Intervention Group Only

1. Anthropometrics of infant (weight, recumbent length)

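### When an intervention infant on a reduced formula volume is removed for missed visits, no step in section 3.3.2 tells the pediatrician that the reduction was recommended

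*Combined protocol and SAP*

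**What the plan says.** Section 3.3.1 gives two grounds for removal. One is failure-to-thrive. The other is "Non-adherence to the study visit schedule characterized by failing to complete" two of the scheduled intervention visits within two weeks of turning 1, 2, 3, 4 and 5 months.

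Section 3.3.2 describes the closing contact: "Study personnel will contact consenting parents by phone notifying them of their removal from the study and the reason for withdrawal". A letter is sent if the parent cannot be reached, and no separate content is given for it. On the pediatrician it says: "If the reason is due to failure-to-thrive, the infant's pediatrician will also be notified". No further data are collected after removal. The template prompt for that section asks for "the follow-up for subjects withdrawn from investigational treatment".

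The treatment here is feeding advice (section 7.2). At or above the 75th weight-for-length percentile, the recommended daily volume is cut by 10%. After a second consecutive month at that level it is based on the "energy requirement (kcal/kg/day) with a 15% reduction in daily volume". The advice has a term: "Recommend formula volumes for the next month based on Visit 2 procedures". It is not a hard cap either: "If hunger cues persist, they will then prepare an additional 1-2 ounces of formula".

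**The concern.** The protocol ties pediatrician notice to the reason for removal, not to what the infant was last advised to take. An infant removed for missed visits can be holding advice to take less than the calculated requirement. On removal the study stops weighing that infant and stops recalculating the volume. The pediatrician then becomes the only source of feeding advice, and no protocol step gives that pediatrician the fact most useful for judging slow growth: that a reduced intake was recommended, and how large it was.

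Only the intervention arm can meet this gap. What is at stake is a small piece of infant safety. The primary endpoint, the analysis and the sample size are not affected.

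**Working it through.** **Step 1: is the handover anywhere else in the protocol?**
- Section 5.4.6: no debriefing, because parents get growth information from the pediatrician. Feeding advice is not mentioned.
- Section 9.1: growth charts are reviewed at visits, and study visits end on removal.
- Section 10.0: faltering could be met by raising intake, but nobody is assigned to do this after removal.
- Section 12.0: parents receive growth data.
- Section 15.4: usual well-child care continues, with no mention of passing on the study volume.

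None of these tells the pediatrician about a reduced volume.

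**Step 2: the plan's own figure.** Section 7.2.2 puts the 10% cut at about 3 oz/day. Check: 0.10 × Table 8 requirement (kcal/day) ÷ 20 kcal/oz, months 1-5. Boys: 0.10 × 560 / 20 = 2.8 up to 0.10 × 634 / 20 = 3.2 oz. Girls: 0.10 × 509 / 20 = 2.5 (2.545) up to 0.10 × 600 / 20 = 3.0 oz. The figure reproduces. At 19 kcal/oz the ounces are about 5% higher (20/19 = 1.05).

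**Step 3: has the advice lapsed by removal?** Nominal removal day = second missed month × 30.44 + 14, so day 105, 136 or 166 for month 3, 4 or 5. The last volume runs to the month after the last attended visit. If months 3 and 5 are missed, the last attended visit is month 4, the volume runs to month 5, and removal comes 14 days later. If months 2 and 3 are missed, the volume lapses about day 61 (2 × 30.44) and removal is at day 105, 44 days later. Across the nine missed-visit pairs in which a volume was given, the gap is 14 or 44 days. An infant who missed months 1 and 2 was never given a volume.

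**Step 4: illustration of size, not needed for the point.** Assumptions: Table 8 median weights, the last anticipated volume followed exactly even after it lapses, no top-ups, no other nutrition. Table 8 requirements in kcal/day, months 1-6: boys 560, 608, 629, 598, 634, 662; girls 509, 556, 585, 569, 600, 626.

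Shortfall = 1 − volume / requirement, where volume = (1 − cut) × requirement in the month after the last attended visit. The requirement at removal is interpolated linearly between months.

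| Missed months | Cut | Volume, kcal (boys / girls) | Shortfall at removal | Shortfall at month 6 |
|---|---|---|---|---|
| 3 and 5 | 10% | 570.6 / 540.0 | 11.8% / 11.8% | 13.8% / 13.7% |
| 2 and 3 | 10% | 547.2 / 500.4 | 11.0% / 13.4% | 17.3% / 20.1% |
| 3 and 4 | 15% | 534.7 / 497.3 | 13.0% / 14.7% | 19.2% / 20.6% |
| 4 and 5 | 15% | 508.3 / 483.7 | 21.4% / 21.0% | 23.2% / 22.7% |

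Worked case, boys, months 3 and 5 missed: 0.90 × 634 = 570.6 kcal. The requirement at day 166 is 634 + (14/30.44) × 28 = 646.9, and 1 − 570.6/646.9 = 11.8%. At month 6, 1 − 570.6/662 = 13.8%.

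The fair comparison is with the same cut kept current. For that boy it is (0.90 × 662 − 570.6) / 20 = 1.3 oz/day. Across all nine pairs the month-6 excess is 1.1-3.2 oz/day, which one to three top-ups of 1-2 oz could offset.

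Months 3 and 5 is the only pair open to a family that attends every study visit due at a well-child age. The control schedule shows which ages those are: "Instead their visits will correspond to usual care well child visits at ages 1, 2, 4, and 6 months".

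**The case against.** The strongest case against is that the advice has already ended. It is given for one month, that month has nominally passed before removal in every pair, and a parent told of removal will largely understand that study advice is over. This stands. A reader might infer that families are left on an open-ended restriction; the documents do not support that. The stop message to parents is therefore close to a matter of wording.

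A reader might also take the larger shortfalls in the table as expected harm. They are not. Section 7.2.2 gives parents a range, not one number, and lets them top up on hunger cues. The larger month-6 figures need a family already removed for non-adherence to follow an outdated volume exactly for weeks or months. Much of the shortfall also arises before removal, so section 3.3.2 does not cause it. In the first three table rows the shortfall at removal (11.0-14.7%) lies within the 10-15% that the trial intends.

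Nor is the infant left unobserved. Section 3.1 requires an intention to attend well-child visits at a Division site through 6 months, and section 15.4 says such care continues. Removal at day 105 falls 5-35 days before the month-4 window (days 110-140). A family that misses only months 3 and 5 is still recalculated at month 4, and is removed 6-44 days before the 6-month window (days 172-210).

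The consent form was not available, so it may say something about stopping.

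What survives is the pediatrician's side. Continued care means that someone is weighing the infant. It does not mean that this person knows a reduced volume was recommended, and neither the one-month term nor the parents' consent form would notify the pediatrician at removal.

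**Conclusion.** The point holds in a narrow form. For an intervention infant last given a 10% or 15% reduced volume and then removed for two missed visits, the study's checks and recalculation stop and no protocol step informs the pediatrician of the reduction. This rests on the text of section 3.3.2 and on the absence of a handover elsewhere in the protocol, not on the illustrative shortfalls.

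The consequence is likely small. How many infants would be affected cannot be estimated, because the documents give neither an expected rate of missed-visit removal nor the share of infants at or above the 75th weight-for-length percentile. This is a cheap improvement to the plan. The documents do not show that removed infants would come to harm.

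**What to change.** Amend section 3.3.2 in two places.

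1. Extend the existing pediatrician notice to any removed intervention infant whose last study recommendation was a reduced volume, whatever the reason for removal. State the last weight, weight-for-length percentile and recommended volume. What the infant is then fed is the pediatrician's decision.
2. Add one line to the parent call and the fallback letter: the study volume no longer applies, and feeding questions go to the pediatrician.

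Infants who never had a reduction, or whose latest recommendation was unreduced, need no extra notice.

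Cost: one short notice per such removal, to a pediatrician expected to be in the same Division, and possibly a line in the consent text. There are no added visits, data collection or staff, and no change to the analysis.

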1.2 Primary Study Endpoints

State the primary endpoints to be measured in the study.

Clinical trials typically have a primary objective or endpoint. Additional objectives and endpoints are secondary. The endpoints (or outcomes), determined for each study subject, are the quantitative measurements required by the objectives. Measuring the selected endpoints is the goal of a trial (examples: response rate and survival).

- Conditional Weight Gain between Birth and Age 6 months

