1.3 Secondary Study Endpoints

State the secondary endpoints to be measured in the study.

- Conditional Weight Gain during the intervention period spanning Ages 1-6 Months
- Mean Weight-for-Length Z-score (WLZ) at Age 6 Months
- Growth Trajectory during the intervention period spanning Ages 1-6 Months (repeated measures of weight-for-length)
- Proportion of Infants with Overweight (Weight-for-Length $\geq 95^{\text{th}}$ Percentile on WHO Growth Charts) at Age 6 months
- Feasibility: a) recruitment, b) ability to give tailored formula volume recommendations, c) visit completion, d) retention through 6 months
- Acceptability: parent adherence to formula volume recommendations as measured by 3 day feeding diaries at 2, 3, 4, 5, and 6 months for the intervention group

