8.3 Statistical methods

Describe the statistical methods (or non-statistical methods of analysis) that will be employed.

We will assess conditional weight gain from birth to 6 months to assess rapid infant growth.^{80,81} Conditional weight gain will be calculated as standardized residuals from the linear regression of weight for age at 6 months on weight for age at birth, with length for age at birth and 6 months and infant age at the 6-month visit entered as covariates. We will explore the moderating role of child sex, delivery mode, and maternal parity on intervention effects. Similar analyses will be conducted for the intervention period spanning ages 1-6 months.

For cross-sectional analyses at age 6 months, ANOVA will estimate the effects of intervention group on mean weight-for-length. Logistic regression will be used to compare intervention effects on the dichotomous outcome of overweight at 6 months.

For growth from 1-6 months, we will fit a repeated measures ANOVA of BMI, with visit and study group as within and between factors, respectively.

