10.0 Risks

List the reasonably foreseeable risks, discomforts, hazards, or inconveniences to the subjects related to the subjects' participation in the research. Include as may be useful for the IRB's consideration, a description of the probability, magnitude, duration and reversibility of the risks. Consider all types of risk including physical, psychological, social, legal, and economic risks. Note: Loss of confidentiality is a potential risk when conducting human subject research.

- If applicable, indicate which procedures may have risks to the subjects that are currently unforeseeable.
- If applicable, indicate which procedures may have risks to an embryo or fetus should the subject be or become pregnant.
- If applicable, describe risks to others who are not subjects.

It is possible that a reduction in formula intake could lead to temporary growth faltering (i.e. failure-to-thrive), though this would be self-limited and could be addressed by subsequently increasing formula intake.

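### Removal from the study also ends data collection, so removed infants have no 6-month growth value and no recorded recovery, and this loss can differ by arm

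*Combined protocol and SAP*

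**What the plan says.** Section 3.3.1 lists criteria for removal from the study, not only from the feeding recommendations. The first begins "Infants exhibiting failure-to-thrive defined as" and covers low weight-for-length and downward crossing of more than two major centile lines after enrolment. The second is failure to complete two "scheduled study intervention visits within 2 weeks of turning 1, 2, 3, 4, and 5 months old". Section 3.3.2 adds: "No further data will be collected on participants that are withdrawn, and these participants will not be replaced". The same section has the pediatrician notified when the reason is failure-to-thrive, and section 9.3 records each growth-failure event on a case report form.

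The schedules differ by arm. Section 7.1: "Control infants will follow the same procedures, but will not have scheduled visits at ages 3 and 5 months". Section 9.4 ties data collection to those schedules.

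The primary endpoint is "Conditional Weight Gain between Birth and Age 6 months". Under section 8.3, "Conditional weight gain will be calculated as standardized residuals from the linear regression of weight for age at 6 months", with 6-month length among the covariates. That section compares the randomised groups but names no analysis set, missing-data method or sensitivity analysis. Section 1.3 lists "d) retention through 6 months" as a feasibility measure. On harm, section 10.0 says: "It is possible that a reduction in formula intake could lead to temporary growth faltering". It describes this as self-limited.

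**The concern.** Whether an infant contributes a 6-month value depends on growth before month 6, and the two arms do not have the same chance of removal.

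- The growth criteria nearly duplicate the growth endpoints, and only the intervention arm receives the calibrated volumes that section 10.0 links to faltering.
- The intervention arm has five growth checks before month 6 and control has three, so more intervention infants can be caught even if the intervention does nothing.
- The missed-visit rule lists months 1 to 5, which is the intervention schedule, and leaves its use in controls unclear.

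Taking the slowest-growing infants out of the intervention arm usually pulls the comparison toward no effect. Missed-visit removal could act in either direction. Separately, the trial could not show whether its one named harm resolved, and section 8.2 intends these data to size the next trial.

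**Working it through.** **Nothing to reproduce.** Section 8.2 sets 60 infants on feasibility, with no power, SD, effect size or dropout rate. The documents give no failure-to-thrive or missed-visit rates. All rates and effects below are assumptions, and so is an allocation of 30 per arm.

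**1. Missed-visit rule.** Assume each visit is missed independently with probability p. With k counting visits,

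P(at least 2 missed) = 1 - (1-p)^k - k·p·(1-p)^(k-1).

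For p = 0.10: with k = 5, 1 - 0.5905 - 0.3281 = 0.081; with k = 3, 1 - 0.729 - 0.243 = 0.028.

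| p | Intervention (k = 5) | Control, own schedule (k = 3) | Control, if the rule covers only the intervention arm |
|---|---|---|---|
| 0.10 | 8.1% (2.4 of 30) | 2.8% (0.8 of 30) | 0% |
| 0.15 | 16.5% (4.9 of 30) | 6.1% (1.8 of 30) | 0% |
| 0.20 | 26.3% (7.9 of 30) | 10.4% (3.1 of 30) | 0% |

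The wording permits either control column.

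**2. Two-week limit against the section 7.2 windows.** The windows for months 2 to 5 are days 42-77, 78-109, 110-140 and 141-171, which is 36 + 32 + 31 + 31 = 130 days. By calendar, an infant turns 2, 3, 4 and 5 months old on days 59-62, 89-92, 120-123 and 150-153, depending on birth date. In-window days more than 14 days from the month birthday for every infant are:

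- month 2: before 59 - 14 = 45 (days 42-44), or after 62 + 14 = 76 (day 77), so 4 days
- month 3: after 92 + 14 = 106 (days 107-109), so 3 days
- month 4: after 123 + 14 = 137 (days 138-140), so 3 days
- month 5: after 153 + 14 = 167 (days 168-171), so 4 days

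The total is 14 of 130. A visit on these days is on time under 7.2 but outside the limit in 3.3.1. Month 1 (days 24-41) has no such day.

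**3. Extra checks, low weight-for-length criterion alone.** Simulated monthly weight-for-length z-scores, SD 1, control mean 0 to 0.5, month-to-month correlation 0.8 or 0.9, removal below -1.645, checks at months 1-5 against 1, 2 and 4:

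- No true effect: 3.9-13.7% removed in intervention, 3.1-10.4% in control.
- True difference of -0.50 z at 6 months: 6.6-19.8% against 3.1-10.5%. Completers show -0.37 to -0.44.
- Across all runs, including a -0.30 z effect, 43-84% of removed intervention infants would be at or above the 5th percentile at 6 months. Under section 3.3.2 that recovery would not be seen.

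**4. Primary endpoint.** This simulation also selects birth weight z at or above 0 (inclusion criterion 2), adds the centile-crossing criterion (off, on the weight-for-length chart, or on the weight-for-age chart, because 3.3.1 does not name the chart), and refits the section 8.3 residual in completers. Correlations are 0.80 to 0.95. The true difference is -0.5 z in weight-for-length.

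- At most 10% of intervention infants removed, crossings counted from month 1: completers show 90-99% of the full difference for a uniform effect, a shift of up to about 0.07 SD.
- 10-34% removed, counted from month 1: 70-89%, a shift of up to about 0.15 SD.
- Counted from birth, which 3.3.1 permits because enrolment can occur in the birth hospitalization: in the least favourable of these settings (mean 0, correlation 0.80, weight-for-length chart), about 67%, a shift of about 0.17 SD with about 34% removed.
- No true effect: a spurious difference of about 0.1 SD in that same setting, and smaller in the others.

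For scale, the standard error of a difference in a standardised residual is about sqrt(2/30) = 0.26. These are examples, not bounds. The percentages depend on the assumed effect: for -0.25 z, counted from month 1, they are 76-99% and 52-77%.

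**The case against.** The strongest reply is that this is a feasibility pilot with no power claim, and that the plan expects few events: section 9.7 calls adverse events infrequent, and section 7.2.2 considers failure-to-thrive unlikely at the chosen reduction. Section 9.8 would suspend the study above 33% failure-to-thrive in the intervention group, so the heaviest scenarios sit at about that trigger. Every shift above is smaller than the standard error. This stands, and the bias argument alone would not carry much weight.

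Harm handling is also partly in place. The event is recorded, the pediatrician is told, and usual care continues (section 15.4). An infant who first meets a growth criterion at the 6-month visit loses no 6-month value. What is missing is narrower: the later course as trial data.

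Three stronger readings are tempting. A reader might infer that the primary comparison is seriously biased; without event rates, the documents cannot show that. A reader might infer that infants are not compared by assigned arm; section 8.3 does compare the study groups formed by randomisation, and only an explicit analysis set is absent. A reader might infer that unequal removal distorts a comparison of retention between arms; no such comparison is planned.

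The reply does not remove the point. A growth endpoint is still named as primary, the data feed the next trial, and even one removed infant leaves the self-limited claim unchecked. Routine measurements probably will exist, since inclusion criterion 8 asks for intended well-child visits at the study practices, but section 3.3.2 as written rules out collecting them.

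**Conclusion.** The point holds as a cheap improvement, not as a flaw that invalidates the trial. As written, the plan makes 6-month growth values missing in a way that can depend on growth and on arm, and it leaves the course of its one named harm outside the trial data. Both follow from the text of sections 3.3.1, 3.3.2 and 7.1 and need no assumption.

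The size does rest on assumptions. The pull on the primary endpoint is small at the event rates the plan expects and becomes material only if removal is common. The missed-visit imbalance depends on the assumed independent miss rates, taken as equal in both arms, and on which reading applies to controls.

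**What to change.** Leave the clinical removal criteria unchanged and amend the data rules:

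1. In 3.3.2, separate stopping the feeding recommendations from stopping data collection. Unless the parent withdraws consent, record 6-month weight and length for every randomised infant, and the outcome of each growth-failure event, from the well-child visit or the medical record.
2. In 8.3, state that all infants are analysed by assigned arm. For values still missing, pre-specify imputation from earlier weights and lengths, with a sensitivity analysis that shifts the imputed values of removed infants.
3. Report removals by arm and reason, separately from family drop-out.
4. Say how the missed-visit rule applies to controls, and reconcile 3.3.1 with the schedules in 7.1 and the windows in 7.2.

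The cost is a short protocol and consent amendment and a record look-up for each removed infant. Some lengths will not be taken on the study stadiometer, some values will still be missing because criterion 8 is only an intention, and the estimate will include infants who stopped the recommendations.
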